**NOTES:**

- T = Table, F = Figure, L = Listing, Y = Yes display generated.
- Stats Analysis = Represents TFL related to any formal statistical analyses (i.e. modelling) conducted.
- Summary = Represents TF related to any summaries (i.e. descriptive statistics) of the observed raw data.
- Individual = Represents FL related to any displays of individual participant observed raw data.

#### 7.3.1. Endpoint / Variables

As specified in the protocol, other secondary endpoints are:

- Change from baseline in clinic FEV1 at 3 hours post study treatment at Week 24
- Change from baseline in St. George's Respiratory Questionnaire (SGRQ) total score at Week 24
- Change from baseline in Asthma Control Questionnaire-7 (ACQ-7) total score at Week 24
- Change from baseline in Evaluating Respiratory Symptoms (E-RS) total score over Weeks 21-24 (inclusive)

### 7.3.2. Summary Measure

- Mean treatment difference on change from baseline in clinic FEV1 at 3 hours post study treatment at Week 24
- Mean treatment difference on change from baseline in SGRQ total score at Week 24
- Mean treatment difference on change from baseline in ACQ-7 total score at Week 24
- Mean treatment difference on change from baseline in E-RS total score over Weeks 21-24 (inclusive).

### 7.3.3. Population of Interest

The secondary efficacy analyses will be based on the ITT population.

### 7.3.4. Strategy for Intercurrent (Post-Randomization) Events

No imputation will be made for missing data.

### 7.3.5. Statistical Analyses / Methods

#### 7.3.5.1. Statistical Methodology Specification

Endpoint

 
• Mean change from baseline in clinic FEV1 at 3 hours post study treatment at Week 24
 

Model Specification

 
• Baseline value is defined in Section 5.2.
 
• The analysis is based on the on-treatment (de jure) type estimand, including on-treatment data collected at Week 24. This is because those participants who withdraw from study treatment will not be able to provide the 3 hours post study treatment assessment in the remainder of the study and so a de facto analysis is not possible.
 
• Change from baseline in clinic FEV1 at 3 hours post study treatment at Week 24 will be analyzed using an Analysis of Covariance (ANCOVA) model
 
• Terms in the model: 
 
○ Dependent Variable: change from baseline in clinic FEV1 at 3 hours post study treatment at Week 24.
 
○ Covariates: 
 
▪ Categorical: treatment group, sex, region, pre-study ICS dosage at screening.
 
▪ Continuous: age, baseline value for clinic FEV1
 
 
 
 
 
• The LS mean FEV1 at 3 hours post study treatment and LS mean change from baseline in FEV1 at 3 hours post study treatment will be estimated using the observed marginal distributions of the study population covariates by inclusion of the OM (observed margins) option in SAS.
 
• The analysis will be repeated for the pooled FF doses, LSMESTIMATE statement will be used with the treatment code as specified Section 7.
 

Model Checking & Diagnostics

 
• Refer to Appendix 8: Model Checking and Diagnostics for Statistical Analyses.
 

Model Results Presentation

 
• Absolute values, change from pre-dose FEV1 and change from baseline in clinic FEV1 at 3 hours post study treatment at Day 1, Weeks 24, 36 and 52 will be summarized.
 
• For the unpooled data, box plots and empirical distribution function plots for the change from baseline in clinic FEV1 at 3 hours post study treatment at Week 24 will be presented.
 

- Least-Squares (LS) means and LS mean change from baseline values for each treatment group will be presented with their associated standard errors. The estimated treatment difference along with corresponding standard error, 95% CI and unadjusted p-value will be presented for all treatment comparisons specified in Section 7.
- The LS mean change from baseline and LS mean treatment differences (and associated 95% CIs) for the comparisons of the two FF/UMEC/VI vs. a FF/VI at a given FF dose will be will also be presented graphically at Week 24, for each of the FF doses in two separate panels.

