7.3.4. Pulmonary Function Tests

Spirometry will be performed at the study site to assess FEV₁ and FVC. At least 3 acceptable spirometry manoeuvres (from a maximum of 8 attempts) should be achieved

on each occasion that spirometry assessments are performed, in accordance with the ATS/ERS standards [Miller 2005]. The highest of 3 technically acceptable measurements will be recorded at each visit:

- **Pre-dose Spirometry:** At Visits 3 through 8/EOS (and the Early Withdrawal Visit, if applicable), subjects should withhold short-acting beta-2-agonists (SABAs) for ≥ 6 hours prior to the clinic visit, if possible. Spirometry assessments must be performed:
 - Between 6am and 11am on the day of the visit.
 - At the same time of day (± 1 hour) as the assessment performed at Visit 3 (the baseline assessment).
 - At least 24 hours after the subject's last morning dose of study treatment on the day prior to the visit.
 - Before the subject's morning dose of study treatment on the day of the visit.
- **Post-dose Spirometry:** At Visits 3, 6 and 8/EOS (and the Early Withdrawal Visit, if applicable), spirometry assessments must be performed 3 hours after the subject's morning dose of study treatment; the assessment performed at Visits 6 and 8/EOS should be performed at the same time of day (± 1 hour) as the assessment performed at Visit 3 (the baseline assessment). At each visit, subjects should withhold short-acting beta-2-agonists (SABAs) between receiving their morning dose of study treatment and completing the spirometry assessments, if possible.

Spirometry equipment will be provided to all sites by a third-party vendor; the same third-party vendor will also centrally analyse the spirometry data from this study. Details on performing the spirometry assessments, including information on the equipment provided and its use as well as specific instructions on performing the spirometry manoeuvres, are documented in the SRM and the third-party vendor manual.

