## 5.2. Baseline Definition & Derivations

For clinic FEV1, the Baseline value is the last acceptable/borderline acceptable pre-dose FEV1 prior to randomized treatment start date (either from pre-dose at Day 1 or pre-bronchodilator at Enrolment Visit or at an unscheduled visit which occurs between the Enrolment Visit and Day 1).

For ACQ, SGRQ, and AQLQ, baseline value for each endpoint is the derived value based on the questionnaire administered at the randomization visit.

For the safety assessments of clinical laboratory, vital signs, and ECGs, the baseline value is the latest value recorded prior to first dose, including pre-dose unscheduled visits.

For diary data the baseline is the average value over the last 14 days prior to randomized treatment start (for more details see Section 5.3.2). If fewer than 7 days of data over the baseline period are available, the baseline value will be set as missing.

If time is not collected, Day 1 clinic assessments (or Day 1 AM diary assessments) are assumed to be taken prior to first dose and used in the derivation for baseline.

All baselines will be referred to as ‘Baseline’ in the summary outputs.

Parameter	Study Assessments Considered as Baseline	
Clinic Assessments		
	Screening	Day 1 (Pre-Dose)
Efficacy		
Trough FEV 1 , FEV 1 3h post study treatment		X*
ACQ-5, ACQ-6, ACQ-7, SGRQ, AQLQ, Global Assessment of Severity		X
Safety		
Clinical Laboratory (incl. total serum IgE and FeNO) †	X	
ECGs†	X	
Vital signs†		X
Diary Assessments		
	Baseline Period	
Efficacy		
Home Daily Trough FEV 1 , Home Daily AM PEF	Last 14 AM assessments during the stabilisation period, including AM assessment on the day of first treatment, prior	

Parameter	Study Assessments Considered as Baseline
	to first dose (i.e., treatment start date per protocol)
Home Daily PM FEV 1 , Home Daily PM PEF	Last 14 PM assessments immediately preceding first treatment during the stabilisation period
%Symptom free days, % rescue medication free days, daily rescue medication use	Last 14 days during the stabilisation period, including AM assessments on the day of treatment i.e., treatment start date per protocol).
E-RS total score and domain scores	Last 14 PM assessments immediately preceding first treatment date during the stabilisation period

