

• An 'on-treatment' analysis will be performed, corresponding to the 'de jure' type estimand analysis specified in the protocol.

○ The endpoint/variable, summary measure and population of interest will be the same as for the primary analysis, as outlined above.

○ The MMRM model fitted will be the same as stated above.

○ Strategy for Intercurrent (Post-Randomization) Events:

▪ An "on-treatment" strategy will be used to handle the intercurrent event of treatment discontinuation. Data collected after treatment discontinuation will be excluded from the analysis and only on-treatment data will be used.

▪ No imputation of missing data is planned. Missing data is assumed Missing at Random (MAR) and handled via Mixed Model Repeated Measures (MMRM) analysis.

 
The same outputs as for the on- and post-treatment (de facto) estimate will be produced

Supportive Statistical analysis - removing sites

The primary model will be repeated excluding participants from sites PPD and PPD
 
The results of the fitted model will be presented. Summaries and figures will not be produced.

Primary Statistical Analyses
Sensitivity analyses – imputation of missing data

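### The 3-hour post-dose FEV1 test at Week 24 uses a single-visit ANCOVA and leaves the Day 1 3-hour value out of the model; a two-visit MMRM would rest on a weaker missing-data assumption at little cost

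*SAP*

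**What the plan says.** SAP section 7.3.5.1 chooses the on-treatment estimand for this endpoint: "The analysis is based on the on-treatment (de jure) type estimand, including on-treatment data collected at Week 24". Its reason is that people who have stopped study treatment cannot give a 3-hour post-dose value, which rules out a de facto analysis. The change from baseline at Week 24 "will be analyzed using an Analysis of Covariance (ANCOVA) model" with treatment, sex, region, pre-study ICS dosage, age and baseline FEV1. Section 7.3.4 adds: "No imputation will be made for missing data".

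Protocol section 7.3.4 schedules the measurement more than once: "At Visits 3, 6 and 8/EOS (and the Early Withdrawal Visit, if applicable), spirometry assessments must be performed 3 hours after" the morning dose. Visit 3 is Day 1, so a 3-hour value is planned after the first randomized dose. The SAP uses that value descriptively only: values "at 3 hours post study treatment at Day 1, Weeks 24, 36 and 52 will be summarized". It is not the baseline, because SAP section 5.2 says the "Baseline value is the last acceptable/borderline acceptable pre-dose" FEV1.

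Under SAP section 11.3.1, Early Withdrawal data on study days 127 to 210 map to Week 24, so an on-treatment 3-hour value from such a visit can enter the ANCOVA. Early Withdrawal values mapped to Week 4 or 12 are excluded for this endpoint.

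For the on-treatment analysis of trough FEV1, SAP section 7.1.6 takes a different route: "The MMRM model fitted will be the same as stated above". SGRQ, in the same section 7.3.5.1, is analysed by MMRM with exactly two visits, Weeks 12 and 24.

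**The concern.** The stated reason supports the on-treatment estimand. It does not explain a one-visit model. The ANCOVA is unbiased for that estimand only if, given treatment and its covariates, having a Week 24 value is unrelated to the outcome. If people with a poor first-dose bronchodilator response stop more often, that condition fails even though the measurement that would reveal it is planned for everyone. A two-visit MMRM also conditions on the Day 1 response, so it needs a weaker assumption.

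At stake are the estimates, confidence intervals and p-values of a named secondary endpoint. The four triple-versus-dual comparisons at a fixed FF dose are the ones of primary interest for it (SAP section 7).

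**Working it through.** **Inputs from the documents.** Protocol section 9.2.1 gives 375 randomized per arm, 10% missing spirometry at Week 24 from study withdrawal, SD 400 mL, difference 100 mL and two-sided 0.05. These are for trough FEV1; no SD, standard error or power is stated for the 3-hour value.

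**Assumed, with ranges.** SD 400 mL is carried over to this endpoint. The correlation ρ between the Day 1 and Week 24 3-hour values, after covariate adjustment, is 0.3 to 0.8. The share d without an on-treatment Week 24 value is 10% or 20%. It may exceed 10%, because people who stop treatment but stay in the study also lack this value.

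**Step 1: the plan's own figure.** With 337 per arm, 100 mL and SD 400 mL, power is 0.9006, matching the stated 90%. Then 337 / 0.9 = 374.4, rounded up to 375. Both reproduce.

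**Step 2: standard error.** With Day 1 seen in all n and Week 24 in m = n(1 − d), the maximum-likelihood Week 24 mean has variance σ²[(1 − ρ²)/m + ρ²/n] = (σ²/m)(1 − ρ²d). Hence

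SE(MMRM) / SE(ANCOVA) = √(1 − ρ²d).

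At d = 10%, SE(ANCOVA) = 400 × √(2/337.5) = 30.79 mL. At d = 20%, it is 400 × √(2/300) = 32.66 mL.

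| ρ | MMRM SE, d = 10% | reduction | power for 100 mL (ANCOVA 0.901) | MMRM SE, d = 20% | reduction |
|---|---|---|---|---|---|
| 0.3 | 30.65 | 0.5% | 0.904 | 32.36 | 0.9% |
| 0.5 | 30.40 | 1.3% | 0.908 | 31.83 | 2.5% |
| 0.7 | 30.03 | 2.5% | 0.915 | 31.02 | 5.0% |
| 0.8 | 29.79 | 3.3% | 0.919 | 30.50 | 6.6% |

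With ρ = 0 or nothing missing, the two are equal. Simulation (3,000 trials per setting, 375 per arm, 10% missing completely at random) gave ratios of 0.995, 0.989 and 0.965 for ρ = 0.3, 0.5 and 0.7, against 0.9955, 0.9874 and 0.9752 from the formula.

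**Step 3: bias under an assumed mechanism.** The true difference is 100 mL at both times. The log-odds of missing Week 24 rise by 1 for each 400 mL lower Day 1 change, equally in both arms, giving about 12% missing.

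| ρ | ANCOVA mean (mL) | MMRM mean (mL) | SE ratio |
|---|---|---|---|
| 0.3 | 97.3 | 99.8 | 0.996 |
| 0.5 | 95.8 | 99.8 | 0.996 |
| 0.7 | 94.6 | 100.2 | 0.993 |

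The shortfall is 2.7 to 5.4 mL, at most 5.4/30.4 ≈ 0.18 standard errors. In this setting the precision gain falls to 0.4% to 0.7%. With a weaker dependence (log-odds slope 0.7 per SD, ρ 0.5 to 0.7, 10% to 15% stopping, Day 1 effect 80 mL), the unadjusted difference among those observed averaged 96.8 to 98.7 mL and the MMRM 99.9 to 100.5 mL.

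**The case against.** The best case for the plan is that the change alters no decision. The endpoint is absent from the hierarchy in SAP section 5.6, the precision gain at the planned 10% is slight, and ANCOVA is valid under missing at random given its covariates. Protocol section 9.4.3 leaves such detail to the SAP. All of this stands.

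The comparison with trough FEV1 also has limits. That MMRM sees Weeks 4, 12 and 24, so it picks up deterioration before stopping. Here the only planned earlier value follows the first dose, 24 weeks before the endpoint. Protocol section 5.6.1 lists adverse events and exacerbations among reasons for stopping, and a Day 1 value says little about those. The protection is formally better but modest in practice. The proposed model would also still leave out Early Withdrawal values mapped to Weeks 4 and 12.

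A reader might infer more than the documents support:

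- **That only people still on treatment at Week 24 are tested.** Not exactly, because on-treatment Early Withdrawal values on days 127 to 210 can enter.
- **That the Day 1 data are ignored.** They are tabulated; they are only absent from the model.
- **That the estimate is seriously biased.** If dropout depended on Day 1 response in the control arm alone, the ANCOVA mean would be 86, 75 and 66 mL for ρ = 0.3, 0.5 and 0.7, with the MMRM at 99 to 100 mL. That is an extreme illustration. Nothing in the documents suggests dependence in one arm only, or shows that stopping depends on first-dose response at all.
- **That the on-treatment estimand is wrong.** The SAP gives a sound reason for it, and the MMRM keeps it.

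**Conclusion.** The point holds as a small, inexpensive improvement. The single-visit ANCOVA drops anyone without an on-treatment value in the Week 24 window, and the planned Day 1 response could be modelled under a weaker assumption. The missing-data argument carries the point more than precision does.

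The size rests on an SD borrowed from trough FEV1 and on a correlation, missing share and dropout mechanism that the documents do not give for this endpoint. The MMRM still assumes missing at random and does not make the analysis a de facto one.

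**What to change.** In SAP section 7.3.5.1, make the main analysis of this endpoint an MMRM of on-treatment 3-hour change from baseline at Day 1 and Week 24. Use the same covariates plus visit, treatment-by-visit and baseline-by-visit, with unstructured covariance, and report the Week 24 contrasts for the comparisons already planned. Enter Day 1 as a repeated response, not a covariate: it follows the first randomized dose, so adjusting for it would remove part of the treatment effect. Keep the ANCOVA as supportive, and state that Week 24 includes Early Withdrawal values mapped there.

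The cost is one SAP paragraph, a matching edit to the model-checking list in section 11.8 and minor programming. No new data are needed. The downside is one more modelled visit than the endpoint strictly requires.

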### Endpoints

- Change from baseline in SGRQ total score at Week 24
- Change from baseline in ACQ-7 total score at Week 24
- Change from baseline in E-RS total score at Week 24

### Model Specification

- Analyses are based on the treatment policy (de facto) type estimand using the pooled FF doses.
- Baseline definitions are provided in Section 5.2.
- The change from baseline for each endpoint will be analyzed using a Mixed Models Repeated Measures (MMRM) model.
- Terms in the MMRM model
  - Period:
    - SGRQ: Clinic visits Week 12 and 24
    - ACQ-7: Clinic visits at Week 4, 12 and 24
    - E-RS: Weeks 1-4, Weeks 5-8, Weeks 9-12, Weeks 13-16, Weeks 17-20, Weeks 21-24.
  - Covariates:
    - Categorical: treatment group, sex, region, pre-study ICS dosage at screening and period.
    - Continuous: age, baseline value
  - Interaction: baseline\*period, treatment\*period
    - Repeated: period
  - All 6-arm data are included in the model.
  - LSMESTIMATE statement will be used with the treatment code as specified Section 7.
  - For the E-RS endpoint, the average treatment effect over the 24-week treatment period will also be obtained from the model and presented in the analysis output.
- The model will be fitted with an unstructured variance-covariance matrix.
- The OM option in SAS will be used to derive the LS means based on the distribution of the covariates observed in the data

#### Analyses of other interest:

- The summaries and analyses will be repeated for the 'de facto' type estimates using the unpooled data.

### Model Checking & Diagnostics

Refer to [Appendix 8](#): Model Checking and Diagnostics for Statistical Analyses.

**Model Results Presentation**

- Absolute values and change from baseline will be summarized by period.
- For the ACQ endpoint, the number and percentage of participants in each control category (see Section 11.6.3) and the change in control category will be presented. A shift table of the number and percentages of participants in each control category relative to baseline will also be presented.
- Boxplots of the change from baseline at each clinic visit will be presented.
- Empirical distribution function plots of the change from baseline at each clinical visit will be presented.
- Least-Squares (LS) means and LS mean change from baseline values for each treatment group will be presented with their associated standard errors for the relevant periods. The estimated treatment difference along with corresponding standard error, 95% CI and unadjusted p-value will be presented for all treatment comparisons specified in Section 2.4 at each timepoint.
- The LS mean change from baseline and treatment differences (and associated 95% CIs) at each timepoint will also be presented graphically.
  - Where unpooled FF is presented the figures will present the comparisons of the two FF/UMEC/VI vs. FF/VI at a given FF dose at each timepoint, with the FF doses in two separate panels.
  - Where pooled FF is presented the figures will present the comparisons of the pooled FF/UMEC/VI vs. FF/VI at a given UMEC dose will be presented graphically at each time point.

## 7.4. Other Efficacy Analyses

An overview of the planned other efficacy analyses is provided below. The full details of data displays are presented in [Appendix 10: List of Data Displays](#).

All analyses will use the de-facto type estimand, unless otherwise stated.

For all non-lung function endpoints, analyses will focus on pooled FF doses. In addition, analyses of exacerbation endpoints and responder rates for ACQ-7, SGRQ and E-RS will present unpooled treatment comparisons.

For the lung function related endpoints only the unpooled analyses will be performed.

The treatment comparisons that will be presented for each endpoint are detailed in [Section 7](#).

Other Endpoint	Absolute					Change from Baseline				
	Stats Analysis		Summary		Individual	Stats Analysis		Summary		Individual
	T	F	T	F	L	T	F	T	F	L
Clinic trough FEV 1 over the first 24 weeks of the treatment period	Y		Y		Y	Y	Y	Y		Y
Home daily trough FEV 1	Y		Y		Y	Y	Y	Y	Y	Y
Home daily PM FEV 1	Y		Y		Y	Y	Y	Y	Y	Y
Annualized rate of severe asthma exacerbations	Y	Y	Y							
Time to first severe asthma exacerbation	Y	Y	Y							
Time to first moderate/severe asthma exacerbation	Y	Y	Y							
ACQ-7, ACQ-6 and ACQ-5 responder	Y		Y	Y						
ACQ-7, ACQ-6 and ACQ-5 Asthma Control	Y		Y	Y						
SGRQ domain scores	Y		Y		Y	Y	Y	Y		Y
SGRQ responder	Y		Y	Y						
E-RS domain scores	Y		Y		Y	Y	Y	Y		Y
E-RS responder	Y		Y	Y						
Asthma Quality of Life	Y		Y		Y	Y	Y	Y		Y

Other Endpoint	Absolute					Change from Baseline				
	Stats Analysis		Summary		Individual	Stats Analysis		Summary		Individual
	T	F	T	F	L	T	F	T	F	L
Questionnaire (AQLQ) total										
AQLQ responder	Y		Y	Y						
Home daily AM PEF	Y		Y		Y	Y	Y	Y	Y	Y
Home daily PM PEF	Y		Y		Y	Y	Y	Y	Y	Y
Symptom-free days	Y		Y		Y	Y	Y	Y		Y
Rescue medication-free days	Y		Y		Y	Y	Y	Y		Y
Daily rescue medication use	Y		Y		Y	Y	Y	Y		Y
Healthcare Outcomes										
Global assessment of severity and response to treatment			Y							
Work Productivity and Activity Impairment-Specific Health Problem			Y							
Unscheduled asthma related healthcare resource utilization			Y		Y					

**NOTES:**

- T = Table, F = Figure, L = Listing, Y = Yes display generated.
- Stats Analysis = Represents TFL related to any formal statistical analyses (i.e. modelling) conducted.
- Summary = Represents TF related to any summaries (i.e. descriptive statistics) of the observed raw data.
- Individual = Represents FL related to any displays of individual participant observed raw data.

**7.4.1. Endpoint / Variables**

As specified in the protocol, other efficacy endpoints are:

- Change from baseline in clinic trough FEV1 over the first 24 weeks of the treatment period (weighted mean)
- Change from baseline in home daily trough FEV1 over the first 24 weeks of the treatment period
- Change from baseline in home daily PM FEV1 over the first 24 weeks of the treatment period
- Annualized rate of severe asthma exacerbations
- Time to first severe asthma exacerbation
- Time to first moderate/severe asthma exacerbation

- Percent of patients meeting a responder threshold of  $\geq 0.5$  points improvement (decrease) from baseline for the ACQ-7 at Week 24
- Percent of patients meeting a responder threshold of  $\geq 0.5$  points improvement (decrease) from baseline for the ACQ-6 at Week 24
- Percentage of patients meeting a responder threshold of  $\geq 0.5$  points improvement (decrease) from baseline for the ACQ-5 at Week 24
- Percentage of patients that have achieved asthma control based on ACQ-7 (i.e. a total score  $\leq 0.75$ ) at both Week 12 and Week 24
- Percentage of patients that have achieved asthma control based on ACQ-6 (i.e. a total score  $\leq 0.75$ ) at both Week 12 and Week 24
- Percentage of patients that have achieved asthma control based on ACQ-5 (i.e. a total score  $\leq 0.75$ ) at both Week 12 and Week 24
- Change from baseline in SGRQ domain scores (symptoms, activity, impact) at Week 24
- Percent of patients meeting a responder threshold of  $\geq 4$  points improvement (decrease) from baseline for the SGRQ total score at Week 24
- Change from baseline in E-RS domain scores (breathlessness, cough and sputum, chest) over Weeks 21-24 (inclusive) of the treatment period
- Percent of patients meeting a responder threshold of  $\geq 2$  points improvement (decrease) from baseline for the E-RS total score over Weeks 21-24 (inclusive) of the treatment period
- Change from baseline in the Asthma Quality of Life Questionnaire (AQLQ) total score at Week 24
- Percent of patients meeting a responder threshold of  $\geq 0.5$  points improvement (increase) from baseline for the AQLQ total score at Week 24
- Change from baseline in morning (AM) pre-dose Peak Expiratory Flow (PEF) over the first 24 weeks of the treatment period
- Change from baseline in evening (PM) PEF over the first 24 weeks of the treatment period
- Change from baseline in the percentage of symptom-free days over the first 24 weeks of the treatment period
- Change from baseline in the percentage of rescue medication-free days over the first 24 weeks of the treatment period
- Change from baseline in daily rescue medication use over the first 24 weeks of the treatment period.
- Unscheduled asthma-related healthcare resource utilization over the first 24 weeks of the treatment period.

